Study Protocol, including Statistical Analysis Plan

Official title:

Development of a Novel Therapeutic for Smoking Cessation

Brief title:

“Test of Novel Drug for Smoking Cessation” ([name], PI)

ClinicalTrials.gov ID: NCT02217527

Protocol Date: Most recent IRB approval--**5/1/2018**

Protocol and Statistical Analysis Plan for

“Development of a Novel Therapeutic for Smoking Cessation”

(NCT02217527): [name] PhD, PI (Univ Pittsburgh)

Scientific Background

Purpose of study: We have partnered with Janssen Research and Development (Johnson & Johnson) to test if an $\alpha 7$ nicotinic acetylcholine receptor (nAChR) positive allosteric modulator (PAM), JNJ-39393406, will promote smoking cessation. Preclinical efficacy/feasibility studies were performed based on highly convincing preliminary data showing that activation of $\alpha 7$ nAChRs decreases rats' motivation to work for nicotine (Brunzell and McIntosh, 2012). A novel, efficient procedure for predicting therapeutic efficacy of smoking cessation drugs (Perkins and Lerman, 2014) will evaluate JNJ-39393406's efficacy in healthy smokers.

Stimulation of $\alpha 7$ nAChRs as a strategy for smoking cessation: Selective stimulation of $\alpha 7$ nAChRs is an innovative strategy for smoking cessation treatment. The highly selective $\alpha 7$ nAChR PAM, JNJ-39393406, could assist individuals in quitting with fewer side-effects than currently available therapeutics. The JNJ-39393406 $\alpha 7$ nAChR PAM proposed ought to work more efficiently and more specifically than an $\alpha 7$ agonist drug in promoting smoking cessation. The JNJ-39393406 PAM does not activate $\alpha 7$ nAChRs on its own, but in binding to an allosteric site (different from the nicotine/ACh binding site) selectively enhances nicotine and ACh activity at the $\alpha 7$ nAChRs. Hence, administration of JNJ-39393406 would be expected to be efficacious for smoking cessation. $\alpha 7$ nAChR PAMs are less likely than a full agonist to lead to neuroadaptations (e.g. of $\alpha 7$ nAChRs) that could result in adverse effects or affect dosing; therefore, JNJ-39393406 would also be expected to exert fewer side-effects than a selective full agonist of $\alpha 7$ nAChRs.

Study Objectives

Aim: To test the proof of principal that JNJ-39393406 promotes smoking cessation. We have developed, tested, and validated an innovative and efficient Phase 2a screening procedure that optimally combines the validity of randomized clinical trials with the practicality of lab- based medication studies. As detailed elsewhere (Perkins & Lerman 2014), it employs a within-subject, cross-over design comparing active versus placebo effects on quitting smoking to maximize statistical power without a large sample. We have demonstrated the sensitivity of this approach in identifying efficacy for biochemically-verified (CO) abstinence in all 3 of the first- line FDA-approved cessation medications, as well as its specificity in identifying lack of efficacy for abstinence in a medication known to not aid cessation. Using this procedure, we will evaluate effects of JNJ-39393406 vs. placebo on short-term smoking abstinence in smokers who already have a high interest

in quitting soon. We predict that, compared with placebo, JNJ-39393406 will increase days of abstinence, identifying initial evidence of efficacy for smoking cessation.

Our main dependent measure is days of very stringent biochemically validated (expired CO<5 ppm) 24-hr smoking abstinence, with post-quit withdrawal and cognitive function as secondary measures. Potential for adverse side-effects will be assessed at each visit. We hypothesize that the number of days of abstinence will be significantly greater for JNJ-39393406 vs. placebo.

Study Design and Methods

Random assignment: Upon entry into the study, subjects will be randomly assigned in double-blind fashion to medication order (active drug then placebo, or vice versa) within the cross-over design. We will use permuted-block randomization to assign subjects to these medication order conditions. The same order assignment will not be repeated more than 3 consecutive times, to prevent an imbalance in the sequence of these orders.

Medication: Active JNJ-39393406 (50 mg tablets), abbreviated here “JNJ” (IND #122957) and matching placebo (both from Janssen Research and Development LLC) will be encapsulated by the WPIC Investigational Drug Service (IDS) research pharmacy. Staff and participants are blind to medication assignment by IDS (i.e. double blind). To start the dose run-up, participants will take one capsule of JNJ-39393406 (50 mg), or identically appearing placebo, once on day 1, incrementing by 50 mg daily to reach 200 mg by day 4. The full dose involves two capsules, each twice per day (100 mg b.i.d. for JNJ), in the a.m. and evening, over the remaining 7 days of that medication condition, including the 5-day practice quit period (Mon-Fri), when they will come to the lab each day to provide CO validation of quit status, plus provide self-reported withdrawal and possible adverse effects. One day will also include computerized test of cognitive processing (see below). One week of *ad lib* smoking follows the first quit attempt phase prior to the dose run-up week with the other condition, to allow separate 3-week tests of each in aiding smoking abstinence.

Procedure: Participation for each subject will be 6 weeks after randomization, involving two 3-week phases, one for each drug condition in this double-blind, crossover procedure. For each phase, visits occur on Mon and on Thurs of the first 2 weeks and Mon-Fri of the third week. CO is assessed upon arrival to each session, along with MNWS withdrawal. Each phase begins with a week of *ad libitum* smoking (baseline, week 1), with drug regimen started on Mon a.m. of week 2 while continuing to smoke (dose run-up). On week 3, they are instructed to try to abstain as of Sun am through the mid-day Fri visit, with CO assessments of quit status on Mon-Fri of week 3. On Mon of week 3, all completed testing of cognitive function (CPT). After Fri of week 3, all then *ad lib* smoke for at least a week to repeat this 3-week phase for the other condition: smoking without drug (i.e. washout; week 4), next dose run-up (week 5), and trying to quit during Mon-Fri (week 6).

Measures:

Smoking outcome. During the “quit week” (week 3) of each condition, the primary outcome of 24-hr abstinence is assessed daily on Mon-Fri by expired-air carbon monoxide (CO) <5 ppm.

Secondary outcomes. Also examined daily are abstinence symptoms on the Minnesota Nicotine Withdrawal Scale (MNWS) (Hughes *et al.* 1991), with each item scored on a 0-100 VAS. In addition, we will assess the Penn Continuous Performance Task (CPT) assessing sustained attention (Kurtz *et al.*, 2001; Gur *et al.*, 2010) on Mon of each quit week. Also assessed daily (Mon-Fri) of the two “quit” weeks (weeks 3 and 6) are medication blinding and side-effects, rated on a 0 to 3 scale (none, mild, moderate, severe). Potential adverse effects will also be assessed by repeat of EKG and lab tests (see end of screening in Eligibility section below) on Fri of week 3 on each condition.

Eligibility Criteria

Randomized will be 60 dependent smokers aged ≥ 18 and < 66 (about 30 women, 30 men) with a high interest in quitting smoking (defined below), i.e. those shown in our prior research to be more sensitive to cessation medication efficacy. All subjects will be smokers with a high interest in quitting soon (within 3 months). Subjects also will be those who have smoked at least 10 cigarettes per day for at least 1 year, with no current use of non-tobacco nicotine products. To obtain 60 participants, we expect to screen about 80 male or female smokers, aged ≥ 18 and < 66 years, living in Allegheny or neighboring counties of the greater Pittsburgh metropolitan region, who do not have significant health problems. We will also assess the Fagerstrom Test of Nicotine Dependence (FTND; Heatherton *et al.* 1991) and other smoking characteristics, but will not select based on these factors. We selected these inclusion criteria because they approximately fit the current FDA-approved indications for smoking-cessation medications, and because we are interested in responses to this active compound, JNJ-39393406, among dependent smokers with an interest in quitting, those most likely to use such medications to help them quit smoking.

Screening will also include assessment of alcohol use via the AUDIT (Saunders *et al.* 1993), as those with scores indicating dependence are excluded. Self-report of no more than 15 drinks/week and 3 drinks on any day in the past week are required. Those not ineligible at screening will receive a physical exam by study physician, including EKG, bloodwork to check liver and kidney function (CBC, etc.), illicit drug screen (other than THC), urine pregnancy test (women), and interview to assess history of psychiatric disorders, suicidal ideation, current major health problems (e.g. heart disease, diabetes) or contraindicated medications (e.g. fentanyl, cyclosporine, pimozide, quinidine).

Statistical Considerations

Analyses will be conducted using IBM SPSS 24.0. Preliminary analyses of variance (ANOVAs) examine effects of sex and of medication order between phases. The primary outcome, number of days abstinent per assessment week (range of 0-5 days), will be analyzed using paired t-tests. Medication condition (active JNJ, placebo) is the within-subjects factor. Generalized estimating equations (GEE) assesses differences between conditions for the secondary outcome of withdrawal, limited to only responses from days in which smoking abstinence is confirmed. Results of cognitive testing are to be examined using paired t-tests for the CPT. Medication condition is a within-subjects factor. Similar to analyses of withdrawal, to detect potential efficacy of conditions on cognitive testing unconfounded by recent smoking, cognitive responses will be analyzed only when CO<10 on both the JNJ and placebo testing sessions, as in prior research (e.g. Perkins, Karelitz, *et al.* 2013b).

References

Brunzell DH, McIntosh JM (2012) Alpha7 nicotinic acetylcholine receptors modulate motivation to self-administer nicotine: Implications for smoking and schizophrenia. *Neuropsychopharmacol.* **37**:1134-1143.

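### Does the stated seven days at full dose conflict with the study calendar in a way that affects the trial's results?

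*Combined protocol and SAP*

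**What the plan says.** The regimen is described in two neighbouring paragraphs of Study Design and Methods.

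- **Medication.** One capsule is taken "once on day 1, incrementing by 50 mg daily to reach 200 mg by day 4". The full dose, taken morning and evening, then runs "over the remaining 7 days of that medication condition, including the 5-day practice quit period (Mon-Fri"). The same paragraph later refers to the run-up as a week.
- **Procedure.** Each phase opens with a baseline smoking week, "with drug regimen started on Mon a.m. of week 2 while continuing to smoke (dose run-up"). In week 3 participants are "instructed to try to abstain as of Sun am through the mid-day Fri visit". The interval before the second condition is "smoking without drug (i.e. washout; week 4").

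Two sets of assessments depend on the end of dosing. Under Measures, "the primary outcome of 24-hr abstinence is assessed daily on Mon-Fri" of the quit week. Under Secondary outcomes, safety is checked by "repeat of EKG and lab tests (see end of screening in Eligibility section below) on Fri of week 3 on each condition". No section gives a clock time for the last dose or names its day outright.

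**The concern.** A reader who lays the Medication sentence on the Procedure calendar finds that the numbers do not add up. Four run-up days and seven full-dose days make 11, and day 11 is Thursday of week 3. Yet the same sentence includes Friday. If seven days are instead counted back from Friday, they begin on Saturday of week 2, and Friday of week 2 has no stated dose.

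This would matter if dosing really stopped on Thursday. Friday carries the fifth of the five carbon monoxide readings that make up the 0-5 day primary outcome. It also carries the end-of-condition EKG and laboratory tests. If these were taken after the last dose had been skipped, the active condition could look slightly weaker, and the safety tests would describe a participant already coming off drug. The start of the drug-free interval before the second condition would also be uncertain.

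**Working it through.** **Inputs.** Day 1 is Monday morning of week 2, and the quit period ends at the mid-day Friday visit of week 3 (Procedure). The 200 mg daily total is reached by day 4, and the full dose is two capsules twice daily for a stated 7 days (Medication).

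**Calendar.**

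| Drug day | Calendar day |
|---|---|
| 1 | Mon, week 2 |
| 4 | Thu, week 2 |
| 5 | Fri, week 2 |
| 6 | Sat, week 2 |
| 8 | Mon, week 3 |
| 11 | Thu, week 3 |
| 12 | Fri, week 3 |

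**Can the stated 7 be reproduced?**

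1. Inclusive days after day 4 through Friday of week 3: 12 - 4 = 8. Not reproduced.
2. The same, counting day 4 as a full-dose day: 12 - 3 = 9. Not reproduced.
3. Seven days forward from day 5: days 5-11, ending Thursday of week 3. This gives 7 but drops Friday, which the sentence includes.
4. Seven days back from Friday of week 3: days 6-12. This gives 7 and keeps Monday to Friday, but day 5 has no stated dose.
5. Elapsed time from Friday morning of week 2 to Friday morning of week 3: 12 - 5 = 7 days exactly. In doses, days 5-11 give 7 x 2 = 14, and Friday morning makes 15. Fifteen doses span 14 half-day intervals, which is 7 days. This gives 7, keeps Monday to Friday and fits a visit at mid-day.
6. Run-up read as the whole of week 2, so that the 7 days are loosely week 3: this gives 7, but it leaves Friday to Sunday of week 2 undescribed and carries dosing past the Friday visit.

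An inclusive count therefore gives 8. The figure 7 can be obtained as elapsed time. The sentence counts the quit period inclusively (five days, Monday to Friday), so reading 5 is plausible but not certain.

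**What each reading does to the assessments.**

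| Reading | Quit-week days on full dose | Friday EKG and laboratory tests | Consistent with the sentence's Mon-Fri? |
|---|---|---|---|
| 8 inclusive days (5-12) | 5 of 5 | on drug | yes |
| 7 elapsed days (Fri a.m. to Fri a.m.) | 5 of 5 | on drug | yes |
| Days 6-12 | 5 of 5 | on drug | yes |
| Week 3 as a whole | 5 of 5 | on drug | yes |
| Days 5-11 | 4 of 5 | after last dose | no |

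Only the last row touches an outcome day. It rests on the one reading that contradicts the sentence being read.

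**Drug-free interval.** Monday of week 5 is day 22. With the minimum one-week washout, the gap from a last dose on Friday morning to the next condition is 22 - 12 = 10 days. From Friday evening it is about 9.5 days. The whole of week 4 is drug-free either way.

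**Statistical Considerations.** The primary analysis is a paired comparison of days abstinent. Neither it nor any secondary analysis uses the number of dosing days, and the document gives no power calculation that could depend on it.

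**The case for a change.** The strongest case for a correction is that the text cannot be read literally. No inclusive count gives exactly seven days that both follow day 4 and contain all of Monday to Friday. No last-dose time is stated, and the day in doubt could be the one with the fifth outcome reading and the safety tests. Supplies counted from the sentence could also run short. Seven days at two capsules twice daily is 7 x 4 = 28 capsules. Dosing through Friday morning needs 15 x 2 = 30, and through Friday evening 16 x 2 = 32.

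Part of this stands. The inclusive count is 8, and the document does not say whether a dose is taken on Friday evening.

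The rest does not carry far. Friday's status is not truly open, because the sentence places Monday to Friday on full dose and week 4 is without drug. The Friday evening dose, if taken, comes after the mid-day visit and its assessments. The document contains no dispensing count, so the capsule totals have nothing to disagree with. Even if a morning dose were missed, the same schedule governs active and placebo in both phases. No bias from unequal scheduling between conditions is shown; at most, drug exposure on one day would be reduced. The document gives no half-life from which to judge any effect.

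**Conclusion.** This is a clerical looseness in a day count, and no change to the plan follows. The size is one day: 8 inclusive days against a stated 7, or 12 drug days against 4 + 7 = 11. On every reading that respects the Monday-to-Friday wording, 0 of 5 outcome days are lost and the Friday safety tests are on drug. No sample size, power or analysis figure moves.

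The conclusion rests on two assumptions. The Monday-to-Friday wording is taken to describe actual dosing, and the Procedure calendar is taken as the schedule that staff follow. Whether a Friday evening dose is taken remains unstated. That bears on the start of the drug-free interval by about half a day, not on any assessment in that condition. The Medication count and the Procedure calendar should be reconciled by the sponsor as a low-priority wording clarification. Which schedule is intended is for the sponsor to say.

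### The withdrawal GEE on abstinent days is a partly between-subject comparison, and the drug-free MNWS scores that would sharpen it are collected but not used

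*Combined protocol and SAP*

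**What the plan says.** Under Study Design and Methods (Procedure), each of the two phases has three weeks, and "visits occur on Mon and on Thurs of the first 2 weeks and Mon-Fri of the third week". On timing, "Each phase begins with a week of *ad libitum* smoking (baseline, week 1), with drug regimen started on Mon a.m. of week 2". The first week of the second phase is week 4, a smoking week without drug that doubles as washout. Because "CO is assessed upon arrival to each session, along with MNWS withdrawal", each phase has two drug-free MNWS readings before its medication starts.

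Under Statistical Considerations, "Generalized estimating equations (GEE) assesses differences between conditions for the secondary outcome of withdrawal, limited to only responses from days" with confirmed abstinence. The section names no covariate, working correlation or period term for this model. Sex and medication order appear only in preliminary ANOVAs. For the CPT, by contrast, a participant is analyzed only if CO is below 10 at both the JNJ and the placebo sessions. The primary outcome, days abstinent out of five, "will be analyzed using paired t-tests". The Study Objectives predict more abstinent days on JNJ than on placebo.

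**The concern.** The plan relies on the crossover for its efficiency: "it employs a within-subject, cross-over design comparing active versus placebo effects on quitting smoking to maximize statistical power without a large sample". That efficiency comes from each person acting as their own control. In the withdrawal analysis this holds only for people with abstinent days under both conditions. A person abstinent under one condition only brings their stable withdrawal level into that side of the contrast, with nothing to cancel it.

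Two things follow. Between-person variation enters the standard error. And if the drug helps some withdrawal-prone smokers abstain who could not do so on placebo, the active side contains more high-withdrawal people, so the drug can look worse on withdrawal than it is. Drug-free MNWS is a direct measure of that stable level, and it is already being collected.

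**Working it through.** The documents give no SD, correlation or abstinence rate for withdrawal, so there is no planned figure to reproduce. The size of the issue rests on simulation with assumed inputs. In every run the true drug effect on withdrawal is zero, and abstinence is less likely in people with higher withdrawal.

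**How many contribute on one side only.** With 60 participants, run A gave about 19 in one condition only and 21 in both; run C gave about 23 and 30. In run B the shares with any abstinent day and with abstinent days in both conditions were 0.91 and 0.71, 0.94 and 0.69, and 0.96 and 0.73 in its three settings with a drug effect on abstinence. The differences of 0.20, 0.25 and 0.23 correspond to 12, 15 and 14 of 60. These counts are simulation outputs, not documented rates.

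**Precision, run A** (60 participants, 150 trials per setting; person SD 15, person-by-phase SD 6, day SD 8 on the 0-100 scale). Entries are the SD of the drug estimate without and with baseline MNWS. Variance cut = 1 − (adjusted SD / unadjusted SD)².

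| Baseline-to-daily correlation | Independence | Cut | Exchangeable | Cut |
|---|---|---|---|---|
| 0.81 | 3.56 to 2.35 | 56% | 2.64 to 2.19 | 31% |
| 0.55 | 3.50 to 2.78 | 37% | 2.63 to 2.58 | 4% |
| 0.40 | 3.57 to 2.99 | 30% | 2.61 to 2.58 | 2% |

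Moving from independence to exchangeable with no covariate gives 1 − (2.64/3.56)² = 45%, 1 − (2.63/3.50)² = 44% and 1 − (2.61/3.57)² = 47%. The working correlation therefore supplies much of the gain.

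**Precision, run C** (60 participants, 500 trials per setting, covariates as participant mean plus phase deviation). At correlations of about 0.87, 0.65 and 0.45, variance fell by 75%, 46% and 19% under independence, and by 54%, 15% and 2% under exchangeable. A further run gave 19-75% and 4-53%. The two-part covariate did not raise variance in either. A single phase-specific covariate can: in one exchangeable run the SD rose from 1.93 to 2.11, and (2.11/1.93)² = 1.20, or 20% more variance.

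**Selection bias, run B** (one data set of 6,000 per setting; person SD 10, phase SD 6, day SD 8; about 1.9 abstinent days on placebo and 2.6 on active; one phase-specific baseline covariate). The baseline-to-daily correlation implied by these inputs is 125.2/√(136 × 200) = 0.76. Entries are the false drug effect in VAS points.

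| Abstinence depends on | Independence | Exchangeable | Independence + baseline | Exchangeable + baseline | Purely within-subject |
|---|---|---|---|---|---|
| Stable trait | 1.63 | 0.25 | 0.27 | 0.22 | 0.04 |
| Trait and phase | 1.79 | 0.73 | 0.39 | 0.39 | 0.56 |
| Trait, phase and day | 2.05 | 1.22 | 0.92 | 0.92 | 1.07 |

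Standard errors were 0.17-0.18 (independence) and 0.16-0.17 (exchangeable) unadjusted, and 0.13-0.14 adjusted, so the smallest entries cannot be told apart from zero. When the drug had no effect on abstinence, every model gave about zero. At 60 participants the standard errors are √(6000/60) = 10 times larger. In the last row the bias is then 2.05/1.7 = 1.2 standard errors unadjusted under independence, 1.22/1.6 = 0.76 under exchangeable, and 0.92/1.3 = 0.71 with exchangeable and baseline. Adjustment helps most when a stable trait drives relapse and least when day-to-day withdrawal does.

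**The case against.** **The bias is not caused by the missing baseline.** A reader might infer that omitting baseline MNWS creates the selection bias and that adding it would remove it. Neither is supported. The bias comes from conditioning on abstinence, and even a purely within-subject fit left up to 1.1 points in run B. The restriction also has a purpose: for the CPT, in a passage that likens its rule to the withdrawal analysis, the plan wants effects not confounded by recent smoking. The bias may also be small against the noise. In run A's most favourable case (correlation 0.81, independence) it fell from about 1.2 to 0.1 points, but 1.2/3.56 is only 0.34 standard errors, and the Monte Carlo error was 3.56/√150 = 0.29 points. All of this stands.

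**Most of the precision comes from the working correlation.** This largely stands, so the fix names it. The covariate still adds a worthwhile amount if drug-free and abstinent-day MNWS are strongly correlated. The documents do not give that correlation.

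**The both-sessions rule might be meant for withdrawal too.** The CPT sentence does say it resembles the withdrawal analysis. But it attaches the both-sessions condition to cognitive responses, while the withdrawal sentence selects days. As written, withdrawal has no such rule.

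**The primary analysis.** A reader might infer that the paired t-test should be adjusted for the change in drug-free CO between weeks 1 and 4. The documents do not support this. The t-test is already within-subject and does not select on abstinence. Week-4 CO is measured after phase-1 treatment and the first quit attempt, so it may carry part of the effect being estimated. In a simulation where each phase-1 abstinent day lowered week-4 CO by 2-3 ppm, the correlation r between the CO change and the change in abstinent days was 0.21-0.26. At 3 ppm the adjusted effect shrank from 0.67 to 0.63 days (0.68 to 0.60 with a sequence term), and power fell from 88% to 85% (82% with the term). The apparent gain, 60/(1 − r²), gives about 62, 66 and 71 effective participants at r = 0.2, 0.3 and 0.4, but r has no source in the documents.

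**The CPT.** No drug-free CPT is described, so there is no baseline to add.

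**Conclusion.** The point holds for the withdrawal analysis only. As written, that contrast mixes within- and between-subject information, and a relevant covariate already collected goes unused. Under assumed inputs, the variance reduction with the recommended exchangeable structure runs from about 2% to 54%, depending almost entirely on how strongly drug-free MNWS predicts MNWS on abstinent days. Under independence, which the plan does not rule out, it runs from 19% to 75%. Selection bias arises only if the drug changes abstinence and withdrawal affects who abstains. Adjustment then lowers it without eliminating it. This is a desirable refinement of one secondary outcome, not a flaw that threatens the trial's main conclusion.

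**What to change.** In the withdrawal GEE, specify an exchangeable working correlation. Add period and two covariates: the participant's mean drug-free MNWS over weeks 1 and 4, and the phase's deviation from that mean. Do not substitute a single phase-specific covariate, which forces one slope on both components.

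Report beside it:
- the unadjusted estimate;
- a version using week-1 MNWS only, because week 4 follows phase-1 treatment and, if the phases run back to back, its Monday visit is three days after the last quit-week visit;
- a sensitivity analysis of participants with abstinent days in both conditions.

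State the number contributing in one and in both conditions, and describe the estimate as conditional on abstinence. Leave the primary paired t-test without the CO covariate.

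The cost is one or two degrees of freedom for the baseline terms and a little more analysis. No new visits or measurements are needed.

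### Does confining the 0-3 side-effect rating to the quit weeks leave the dose run-up without a safety assessment?

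*Combined protocol and SAP*

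**What the plan says.** Four places in the combined protocol and SAP bear on when side-effects are recorded.

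- **Study Objectives** makes a general commitment without an instrument: "Potential for adverse side-effects will be assessed at each visit".
- **Study Design and Methods, Medication** describes the escalation ("incrementing by 50 mg daily to reach 200 mg by day 4"). It says that at the daily visits of the practice quit period participants give CO readings, "plus provide self-reported withdrawal and possible adverse effects".
- **Study Design and Methods, Procedure** sets the calendar for each phase: "visits occur on Mon and on Thurs of the first 2 weeks and Mon-Fri of the third week". For every session it names two measures: "CO is assessed upon arrival to each session, along with MNWS withdrawal".
- **Measures, Secondary outcomes** names the graded rating, from none to severe. It is recorded daily, Monday to Friday, in the quit "weeks (weeks 3 and 6) are medication blinding and side-effects, rated on a 0 to 3 scale". The same paragraph adds a second safety check, on Friday of the quit week in each condition: "Potential adverse effects will also be assessed by repeat of EKG and lab tests".

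Statistical Considerations gives analyses for days abstinent, for withdrawal (GEE "assesses differences between conditions for the secondary outcome of withdrawal") and for the CPT. It gives none for side-effects.

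**The concern.** Withdrawal has a named scale at every session, but side-effects have a named scale only in weeks 3 and 6. A reader who takes the Secondary outcomes paragraph as the full schedule would conclude that nothing graded is collected while the dose is being raised, including the Thursday visit on the day the full daily dose is reached. The repeat EKG and laboratory tests also come later, at the end of the quit week.

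If so, a side-effect that came and went in the first week of capsules, or that led someone to stop before the quit week, might never reach the graded data. Without an off-drug rating, change from baseline within a phase could not be graded either. This would matter because low side-effect burden is part of the scientific rationale for the compound, and a rating not collected cannot be recovered afterwards.

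**Working it through.** The documents state no visit total or other figure on this point, so there is nothing to reproduce. The check is a count from the Procedure calendar, followed by a reading of the statements together.

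**Visits.** Each phase has 2 + 2 + 5 = 9 visits, and there are two phases: 2 × 9 = 18.

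**Visits with the 0-3 rating.** 5 per quit week × 2 = 10. Without a stated graded rating: 18 − 10 = 8, or 8/18 = 44%.

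**What the 8 visits are.**

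| Weeks | Visits | Status |
|---|---|---|
| 1 and 4 | 4 | Off drug (baseline, washout) |
| 2 and 5, Monday | 2 | Capsules start that morning; before or after the visit is not stated |
| 2 and 5, Thursday | 2 | On capsules |

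The visits on capsules without a stated grade are therefore 2 of 18 (11%) if the Monday visit precedes the first capsule, and 4 of 18 (22%) if it follows. Per phase this is 1 of 6 on-capsule visits (17%) or 2 of 7 (29%). One phase is placebo, so on active drug it is 1 or 2 visits per participant. With 60 randomised, 8 × 60 = 480 person-visits falls to 120-240 on capsules and 60-120 on active drug.

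**Timing.** With Monday of week 2 as day 1, Thursday is day 4 and Monday of week 3 is day 8. The first scheduled graded rating therefore follows 7 days of capsules, of which days 4 to 7 (4 days) are at the full daily dose.

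**Do the statements conflict?** Study Objectives covers every visit without qualification. The Secondary outcomes paragraph gives a scale and a daily frequency for the quit weeks and does not say that side-effects are recorded only then. The MNWS shows the same drafting pattern: Procedure places it at every session, while Secondary outcomes mentions only daily examination. General collection is stated in one place and outcome detail in another. Read together, the text gives an enquiry at all 18 visits and a graded form at 10 of them.

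**Would effects on days 1 to 7 be lost?** Only from the graded data, and only if the rating covers current symptoms. No recall window is given. A day-8 rating that looked back to the previous visit (Thursday, day 4) would pick up some of them.

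**Is a baseline missing?** The planned contrast is active against placebo within participant, and the placebo quit week supplies the comparison. No within-phase change in side-effects is planned. The EKG and laboratory tests repeat those done at screening, so they do have a pre-drug reference.

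**The case for a change.** The best argument for a change is that the run-up is the only time participants take capsules while smoking freely. Every scheduled graded rating falls when they are trying to abstain, so withdrawal symptoms can be mistaken for drug effects. The placebo quit week removes this cleanly only if abstinence is similar in the two conditions, and the trial hypothesises that it is not. Run-up ratings would largely avoid the problem, using an existing form at visits that already take place. Side-effects also sit under the Secondary outcomes heading, and staff cannot tell from the text which form to complete at a run-up visit.

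Part of this stands. The instrument at those visits is unnamed, and graded run-up data would be informative. But withdrawal is measured separately on the MNWS at every session, which helps to separate the two kinds of symptom. Study Objectives names only withdrawal and cognitive function as secondary measures and gives side-effects a sentence of their own. No formal side-effect comparison is specified that differential abstinence could distort. Grading all 18 visits would be a reasonable design preference. It would not correct an error.

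**Conclusion.** The concern does not call for a change. The count of 8 ungraded visits in 18 is right, but it overstates the gap, which is an unnamed instrument at 2 to 4 of 18 visits on capsules (1 or 2 per participant on active drug) and at 4 off-drug visits. Side-effect assessment is promised at all of them. Followed as written, the trial loses no stated comparison, and its primary outcome, days abstinent, is untouched. Staff can fill the gap sensibly, either with the existing 0-3 form or with an open enquiry at the remaining visits.

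This rests on three assumptions: that the commitment in Study Objectives is carried out as stated; that the calendar is the stated two phases of nine visits, excluding screening and any extension of the washout; and that side-effects are reported descriptively, since no analysis is specified. If the trial were to make a formal tolerability claim covering the escalation period, the missing grades there would carry more weight.
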